5. STUDY CONDUCT

5.1 Restrictions during the study

Patients should not donate blood or bone marrow at any time during the study period.

There are no study-specific dietary or activity restrictions other than those typical for this patient population.

Restrictions regarding concomitant medications are described in Section 5.6.

5.2 Patient enrolment and randomisation

The Principal Investigator or delegate will:

- 1. Obtain signed informed consent from the potential patient and/or their legal representative before any study specific procedures are performed
- 2. Determine patient eligibility. See Sections 4.1 and Section 4.2.
- 3. Assign (using the Interactive Voice Response System/Interactive Web Response System [IVRS/IWRS], see Section 5.2.1) potential patients a unique enrolment number, beginning with 'E#'
- 4. Assign enrolled patient a unique randomisation code (patient number) obtained from IVRS/IWRS.

If a patient withdraws from participation in the study, then his/her enrolment/randomisation code cannot be reused.

5.2.1 Procedures for randomisation

Randomisation codes will be assigned strictly sequentially within each centre as subjects become eligible for randomisation. Randomisation codes will be generated in blocks to ensure approximate balance (1:1) between the two treatment arms. Once a block is exhausted, the next available block will be allocated by IVRS/IWRS system to a centre upon their next randomisation. Approximately 13600 patients will be randomised in this study.

At Visit 1 for patients who fulfil all the eligibility requirements, the investigator will access the IVRS/IWRS. The IVRS/IWRS will allocate a randomisation code and provide the investigator with unique treatment pack identification (ID) numbers for that patient for the Visit 1 supply of medication. Following randomisation, the first dose of study medication will be administered to the patient as soon as possible.

The randomisation codes will be computer generated by AstraZeneca R&D using the AZ Global Randomisation system (GRand) and loaded into the IVRS/IWRS database.

5.3 Procedures for handling patients incorrectly enrolled or randomised

Patients who fail to meet the inclusion/exclusion criteria should not, under any circumstances, be enrolled or receive study medication. There can be no exceptions to this rule.

The following steps should be taken in the event that a patient who does not meet inclusion/exclusion criteria is found to have been inadvertently enrolled in an AstraZeneca study.

- (a) The investigator or monitor should inform the AstraZeneca study team physician immediately. Ensuring patient safety must always be the number one priority.
- (b) Study treatment must be discontinued in all cases where continued treatment is deemed to pose a safety risk to the patient. After a discussion between the study team physician and investigator, a decision may be reached that the patient should discontinue study medication. The rationale for discontinuing study therapy must be clearly documented. The patient should remain in the study for follow up in accordance with defined study procedures including follow-up on endpoints through the end of the study consistent with the intention-to-treat principle.
- (c) In those cases where continuation of study therapy is judged not to present a concern related to safety and disease management, the rationale for continuing study therapy must be clearly documented. The patient should continue follow up in accordance with defined study procedures.

5.4 Blinding and procedures for unblinding the study

5.4.1 Methods for ensuring blinding

The two medications to be administered in the study have different appearances. Due to this and the different dosing schedules, all patients will take either ticagrelor/matching placebo or ASA/matching placebo in a double-dummy fashion to maintain the blinding. Each pack will be labelled with a unique kit ID number that will be used to assign the treatment to the patient but will not indicate treatment allocation to the investigator or patient. The study drug dosing regimens are:

- 1. ticagrelor 90 mg and ASA placebo in the morning, ticagrelor 90 mg in the evening or
- 2. ticagrelor placebo and ASA 100 mg in the morning, ticagrelor placebo in the evening

No member of the extended study delivery team at AstraZeneca, personnel at investigational centres or any CRO handling data will have access to the randomisation scheme during the conduct of the study, with the exception of the Supply Chain Study Management department, and the Patient Safety department at AstraZeneca.

A DMC will review efficacy and safety data on a periodic basis, including the incidence of AEs and safety assessments to ensure the ongoing safety of study patients. An independent statistician will be contracted to provide the DMC with essential safety and efficacy data during the study. The DMC responsibilities, authorities, and procedures will be documented in a DMC charter. The personnel involved in the clinical study at AstraZeneca will remain blinded to these analyses and will have no knowledge of the results presented to the DMC.

5.4.2 Methods for unblinding the study

Individual treatment codes, indicating the treatment for each randomised patient, will be available to the investigator(s) or pharmacists, from the Interactive Voice Response System/ Interactive Web Response System (IVRS/IWRS). Routines for this will be described in the IVRS/IWRS user manual that will be provided to each centre.

The treatment code should not be broken except in medical emergencies when the appropriate management of the patient requires knowledge of the treatment. The AstraZeneca physician or delegate should be consulted whenever possible prior to the investigator breaking the blind. The investigator documents and reports the action to AstraZeneca, without revealing the treatment given to the patient to the AstraZeneca staff. The number of individuals at the study site who become aware of the treatment status should be kept to an absolute minimum including keeping the patient blinded if possible. Treatment with study medication should be continued if considered appropriate.

AstraZeneca retains the right to break the code for serious adverse events (SAEs) that are unexpected and are suspected to be causally related to a study drug and that potentially require expedited reporting to regulatory authorities. Treatment codes will not be broken for the planned analyses of data until all decisions on the evaluability of the data from each individual patient have been made and documented.

5.5 Treatments

5.5.1 Identity of investigational product(s)

Table 3 Identity of study medication

Study Medication	Dosage form and strength	Manufacturer
Ticagrelor 90 mg	Plain, round, yellow, film- coated tablet, 90 mg	AstraZeneca
Ticagrelor 90 mg placebo	Plain, round, yellow, film- coated tablet, placebo to match 90 mg	AstraZeneca
Acetylsalicylic acid 100 mg	Plain, round, white, enteric coated tablet, 100mg	Bayer
Acetylsalicylic acid placebo	Plain, round, white, enteric coated tablet, placebo to match 100 mg	AstraZeneca

5.5.2 Doses and treatment regimens

At Visit 1 (randomisation) eligible patients will be randomly assigned to 1 of 2 treatments:

- Treatment 1: ticagrelor 180 mg (two 90 mg tablets) with placebo for ASA loading dose on Day 1, followed by 90 mg twice daily given orally together with placebo for ASA once daily.
- Treatment 2: ASA 300 mg (three 100 mg tablets) with placebo for ticagrelor loading dose on Day 1, followed by 100 mg daily given orally together with placebo for ticagrelor twice daily.

Randomisation and treatment pack assignment will be managed via the IVRS/IWRS, and the first dose of study medication should be taken at Visit 1. Subsequent maintenance doses should be taken morning and evening, at approximately 12-hour intervals, for the remainder of the treatment period. If the patient is randomised and takes the loading dose before 2PM on Day 1, the first maintenance dose of ticagrelor/ticagrelor placebo should be given before the patient goes to sleep on Day 1, at least 6 hours after the loading dose; if the loading dose is taken after 2PM on Day 1, the subject should take the first maintenance dose of ticagrelor/ticagrelor placebo in the morning on Day 2 as early as possible.

All patients should continue study treatment for 90 days. At the end of 90 days of study treatment, patients will be treated with standard of care therapy of the Investigator's choice and followed for 30 days.

5.5.3 Additional study drug (NA)

5.5.4 Labelling

Labels will be prepared in accordance with Good Manufacturing Practice (GMP) and local regulatory guidelines. The labels will fulfil GMP Annex 13 requirements for labelling. Label text will be translated into local language.

5.5.5 Storage

All study drugs should be kept in a secure place under appropriate storage conditions. The study medication label on the study supplies specifies the appropriate storage conditions.

5.6 Concomitant and post-study treatment(s)

Recording of concomitant medications will be made at each visit. Medication use 1 month before the study and until the end of the study will be recorded. All ASA containing medication will be captured on a separate module in the eCRF with route of administration and total daily dose. All other concomitant medication will be captured (without total daily dose and route of administration) on a separate module in the eCRF.

5.6.1 Oral antiplatelet and parenteral thrombolytic therapies

Concomitant dual antiplatelet therapy at start of study: Patients requiring dual antiplatelet therapy (eg, ASA plus clopidogrel, ASA plus prasugrel, ASA plus ticagrelor, or ASA plus dipyridamole) will be excluded at randomisation, as the purpose of this study is to primarily test the benefits of mono-antiplatelet therapy. However, after randomisation, patients who

develop an indication (ACS or Percutaneous coronary intervention (PCI)) for dual antiplatelet therapy must discontinue study therapy and be treated with standard of care.

Anticoagulation therapy: Neither high dose thrombosis treatment nor low dose thrombosis prevention treatment with low molecular weight heparins (LMWH) or unfractionated heparins is allowed as concomitant treatment in the SOCRATES study. All other anticoagulation therapy is also prohibited as concomitant medication. If a medical indication for anticoagulation therapy occurs during the study, the study medication should be temporarily discontinued and restarted when there is no longer an indication for such treatment.

Concomitant intravenous or intra-arterial thrombolytics: Receipt of any intravenous or intra-arterial thrombolytic therapy within 24 hours prior to randomisation is prohibited. After randomisation, if patient requires intravenous or intra-arterial thrombolytic therapy, the study medication must be discontinued for at least 24 hours.

5.6.2 Non-steroidal anti-inflammatory drugs (NSAIDs)

Clinical experience with NSAIDs in combination with ticagrelor is limited at this time. Short-term treatment with NSAIDs up to 7 days is allowed during the study at the investigator's discretion. However, chronic daily dosing with non-selective NSAIDs (eg, patients with rheumatoid arthritis) may increase the potential for gastrointestinal bleeding so either alternative therapy or concomitant acid suppression therapy is recommended. Treatment with selective cycloxygenase-2 inhibitors is permitted, although use is cautioned.

5.6.3 Digoxin and other p-glycoprotein interactions

Ticagrelor modestly increases digoxin levels. Therefore digoxin levels should be monitored closely following initiation of study medication and with any change in study medication. Other p-glycoprotein substrates may be expected to have similar changes in pharmacokinetics. For additional details please see the Investigator's Brochure.

5.6.4 CYP450 interactions

5.6.4.1 CYP3A inhibitors

Strong inhibitors of this enzyme (eg, ketoconazole, itraconazole, voriconazole, telithromycin, clarithromycin [but not erythromycin or azithromycin], nefazadone, ritonavir, saquinavir, nelfinavir, indinavir, atazanavir, or over 1 litre daily of grapefruit juice) should not be coadministered with ticagrelor as plasma levels of ticagrelor would be substantially increased.

5.6.4.2 CYP3A substrates or inducers

Concomitant therapy with simvastatin or lovastatin at doses higher than 40 mg daily is not permitted since administration with ticagrelor will result in higher serum concentrations and may put patients receiving more than 40 mg per day of simvastatin or lovastatin at increased risk of statin-related adverse effects. There are no restrictions to other statin therapies (ie, doses of simvastatin or lovastatin ≤40 mg daily or any dose of any other statin is permitted). Investigators are advised to check lipid levels and adjust statin dosages per local practice and

appropriate guidelines. Standard monitoring of patients for possible statin-associated myopathy should be conducted.

Co-administration of ticagrelor with strong inducers of CYP3A also should be avoided (eg, rifampin/rifampicin, rifabutin, phenytoin, carbamazepine, phenobarbital).

Discontinuation of study medication is up to the judgment of the investigator. If continued antiplatelet medication is judged necessary, there may be a need for extra caution regarding bleeding tendency. The investigator should document the use and duration of all treatments (including CYP3A substrates and inducers) in the eCRF.

5.6.5 Surgery

Ticagrelor should be discontinued at least 5 days prior to any surgery. In particular, cardiac surgery and non-cardiac surgery with potential for major bleeding should be performed at least 5 days after stopping study medication. There is a trade-off between stopping study medication too early and risking thrombotic events versus continuing treatment too close to surgery and risking haemorrhage. Thus, it is also recommended that study medication not be discontinued for significantly longer than 5 days so as to minimize the risk of thrombotic complications while off study medication.

Other medication, which is considered necessary for the patient's safety and well being, may be given at the discretion of the investigator and recorded in the appropriate sections of the eCRF.

After surgery, study medications should be restarted when the risk of bleeding is deemed low in the judgment of the investigator, and the investigator should record all peri-procedural bleeding events.

5.6.6 Other surgery and invasive procedures

For other surgery or other invasive procedures such as coronary angiography or PCI, study medication may be continued or interrupted temporarily at the discretion of the investigator. As with all other surgeries, investigators should collect and record all peri-procedural bleeding events.

After the surgery or procedure, study medications should be restarted (if interrupted) as soon as possible.

Other medication, which is considered necessary for the patient's safety and well being, may be given at the discretion of the investigator and recorded in the appropriate sections of the eCRF.

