5.8.1 Temporary discontinuation from study medication

If study drug must be temporarily discontinued, restart it as soon as possible.

- Severe thrombocytopenia (platelet count <50,000/uL). Patients may restart study medication once the severe thrombocytopenia resolves
- Surgery or procedures associated with major haemorrhage, see Section 5.6.5
- Major bleeding, see Section 6.4.6.4

- Need of treatment with prohibited concomitant medications, see Section 5.6
- For other surgery or other invasive procedures, study medication may be continued or interrupted temporarily at the discretion of the investigator, see Section 5.6.6.

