5.8.2 Permanent discontinuation from study medication

- Patient decision. The patient is at any time free to discontinue treatment, without prejudice to further treatment
- Investigator's decision, including but not limited to these examples:
 - 1. Incorrectly enrolled patient in whom the inclusion/exclusion criteria violation would put the patient at undue risk
 - 2. Adverse response thought to be related to the study medication for which the investigator thinks continued treatment may put the patient at undue risk
 - 3. Adverse event for which the investigator thinks continued treatment may put the patient at undue risk
 - 4. Severe non-compliance to study protocol
 - 5. Pregnancy
 - 6. Atrial fibrillation for which the patient receives anticoagulation therapy

Discontinuation of study medication does not mean discontinuation of follow-up or termination of study participation. Study assessments or telephone follow-up should be continued in all cases if possible, see Sections 5.8.3 and 5.9.

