6.2.3 Protocol procedures

Patients will have routine visits and procedures as outlined in Section 3.1. Any new suspected endpoint events, non-serious AEs of interest, DAEs, SAEs, and current medications will be recorded in the eCRF. It will be the responsibility of the Investigator to obtain all necessary source documents including medical records from institutions where a hospitalisation may have occurred.

If the patient experiences a suspected clinical efficacy endpoint event or a bleeding event, the following actions should be taken whenever possible and in accordance with current guidelines and local practice standards:

Symptoms of cardiac ischaemia (ie, potentially representing unstable angina or MI):

- Cardiac biomarkers of necrosis (troponin and/or CK-MB) should be collected serially and measured by local labs according to local standards for at least 24 hours.
- A standard 12-lead ECG should be obtained during or as soon as possible after the episode of ischaemia and serially according to local standards until resolution of symptoms.

Coronary Revascularisation (ie, PCI or Coronary Artery Bypass Graft [CABG]):

- Cardiac biomarkers of necrosis (troponin and/or CK-MB) should be measured locally immediately before the procedure and serially (every 8 hours x 3 or until hospital discharge) after the procedure.
- A standard 12-lead ECG should be obtained before the procedure, immediately post-procedure, and, if possible, in the morning following the procedure.
- For patients undergoing major surgery, all banked blood products administered (ie, the number of packed red blood cell or whole blood transfusions [units transfused and volume in mL], fresh frozen plasma [volume in mL], platelets [units transfused and volume in mL] and cryoprecipitate [volume in mL]) and those undergoing CABG, the chest tube output in the first 24 hours should be noted.

Focal neurological symptoms (ie, potentially representing stroke or transient ischaemic attack):

- Complete neurological exam
- Brain imaging (CT scan or MRI)

Bleeding (either unexpected or of unanticipated quantity):

- Record last stable haemoglobin before start of bleeding (or haematocrit if haemoglobin unavailable). Haemoglobin (or haematocrit if haemoglobin unavailable) should be measured locally serially until resolution of the bleeding.
- Record the date, time and number of all banked blood products administered.

Patient health related quality of life

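### Protocol sections 5.6.1 and 5.6.6 give opposite study-drug rules for PCI, so a site following 5.6.6 could give blinded drug on top of open-label dual antiplatelet therapy

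*Protocol*

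**What the plan says.** Four places in the protocol bear on study drug around a PCI.

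- **Section 5.6.1** excludes patients who need dual antiplatelet therapy at randomisation, because the trial is meant to test single-agent treatment. For the period after randomisation, patients who "develop an indication (ACS or Percutaneous coronary intervention (PCI)) for dual antiplatelet therapy must discontinue study therapy" and move to standard of care. No duration or restart condition is given for this stop. For anticoagulants the same section does give one: "the study medication should be temporarily discontinued and restarted when there is no longer an indication for such treatment". For thrombolysis it sets a minimum interruption of 24 hours.
- **Section 5.6.6** covers other surgery and invasive procedures. For procedures such as "coronary angiography or PCI, study medication may be continued or interrupted temporarily at the discretion of the investigator". It adds: "After the surgery or procedure, study medications should be restarted (if interrupted) as soon as possible". It also says: "Other medication, which is considered necessary for the patient's safety and well being, may be given at the discretion of the investigator".
- **Section 5.8.1**, on temporary stops, repeats this for other procedures: "study medication may be continued or interrupted temporarily at the discretion of the investigator, see Section 5.6.6". The bullet just above lists a need for prohibited concomitant medication as a reason for a temporary stop.
- **Section 5.8.2** gives examples of permanent discontinuation and says they are not exhaustive. One is "Atrial fibrillation for which the patient receives anticoagulation therapy". Dual antiplatelet therapy, ACS and PCI are not among them.

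**The concern.** For the same clinical event, one section makes stopping study drug mandatory and another makes continuing it optional, with a prompt restart if it was interrupted. An investigator who looks up the section on invasive procedures finds PCI named there, with permission to continue and no pointer to the dual-therapy rule.

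Bleeding safety is the main stake. Section 1.4 calls bleeding the most important risk of antiplatelet agents, especially in dual therapy. A patient who has a PCI and receives open-label aspirin plus a P2Y12 inhibitor, while still on blinded drug, would be more heavily treated than either trial regimen intends. Because treatment is blinded, the investigator would not know whether the extra agent is ticagrelor or aspirin.

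Consistency of conduct is the second stake. With about 1000 centres, different sites can reasonably apply different rules. The safety analysis set (section 12.1.2) censors patients 7 days after the last dose, so a site's choice to stop or continue at PCI also decides whether a later bleed is counted.

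**Working it through.** The protocol states no figure for this point, so the check is mainly a comparison of text, followed by a short dose calculation.

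**1. The two rules compared**

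| Question | Section 5.6.1 | Section 5.6.6 |
|---|---|---|
| Is PCI named? | Yes, as an indication for dual antiplatelet therapy | Yes, as an example of an invasive procedure |
| What happens to study drug? | Must be discontinued | May be continued or briefly interrupted |
| Who decides? | No discretion | The investigator |
| Restart? | Not stated | As soon as possible |
| Other treatment? | Standard of care | Other necessary medication, with no exception for antiplatelets |
| Reference to the other section? | None | None |

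The second row cannot be satisfied both ways when a PCI brings a need for dual therapy. Section 5.6.1 treats PCI as creating that need.

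**2. Does nearby text settle it?**

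- Section 5.8.1 opens by asking for the earliest possible restart and then points to 5.6.6 without a dual-therapy exception. Its prohibited-medication bullet would lead a careful reader to stop. However, it belongs to a list of temporary stops, sits beside the bullet that permits continuation, and leaves the permission for PCI in 5.6.6 untouched.
- Section 5.8.2 does not name dual therapy. As its list is open-ended, the omission is not a contradiction, but it gives no help.

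**3. Can the situation arise?**

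Yes. Section 6.2.3 prescribes biomarker and ECG schedules for PCI during the study. Exclusion criterion 4 removes only planned revascularisation that requires study drug to be halted within 7 days of randomisation. Unplanned PCI, and PCI planned for later, remain possible.

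**4. What would a patient receive under 5.6.6?**

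Inputs: blinded ticagrelor 90 mg twice daily or ASA 100 mg once daily (section 5.5.2); ASA plus clopidogrel, prasugrel or ticagrelor among the dual therapies named in 5.6.1; overdose defined as more than 4 ticagrelor tablets a day in the maintenance phase (section 13.2).

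- Ticagrelor arm, open-label ASA plus clopidogrel or prasugrel: 1 blinded + 2 open-label = 3 antiplatelet drugs, of which 2 are P2Y12 inhibitors.
- ASA arm, any of these dual therapies: blinded aspirin plus open-label aspirin, so aspirin twice, plus a P2Y12 inhibitor.
- Ticagrelor arm, open-label ASA plus ticagrelor. *Assumption:* open-label ticagrelor at 90 mg twice daily, the dose section 1.1 describes on background aspirin in the ACS trial.
  - Blinded: 2 × 90 = 180 mg/day
  - Open-label: 2 × 90 = 180 mg/day
  - Total: 180 + 180 = 360 mg/day; 360 / 180 = 2.0 times the study dose
  - Tablets: 360 / 90 = 4 a day. The definition needs more than 4, so this would not count as an overdose.

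**5. How many patients?**

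The protocol gives no PCI frequency, so no count can be derived.

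**The case against.** The best defence is that the two sections do different jobs. The trigger in 5.6.1 is an indication for dual antiplatelet therapy, with ACS and PCI given in brackets as its sources. Section 5.6.6 follows the surgery section, groups PCI with angiography, and deals with whether to hold drug around a procedure. On that reading the specific mandatory rule limits the general permissive one. The prohibited-medication bullet in 5.8.1 and exclusion criterion 1 confirm that the trial does not want added antiplatelets. The sentence on other medication also appears in 5.6.5 and does not expressly lift the restriction in 5.6.1. The unqualified stop in 5.6.1, beside explicitly limited stops for anticoagulants and thrombolysis, may itself suggest no restart. Finally, the 360 mg/day case needs several things to coincide, including an investigator who adds open-label ticagrelor knowing that the blinded drug may be ticagrelor.

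Much of this stands. A harmonising reading exists, the 5.8.1 bullet is a real partial safeguard, and the dose example illustrates a worst case rather than an expected one. It does not remove the conflict. Section 5.6.1 names PCI itself, 5.6.6 names PCI without exception, and each site has to work out the order of precedence for itself.

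**Conclusion.** The concern holds. Sections 5.6.1 and 5.6.6 give conflicting instructions for study drug in a patient who has a PCI after randomisation, and nothing in the protocol says which prevails. The conflict should be corrected because it allows an unsafe combination. It does not undermine the trial's main result: the efficacy analysis counts events whether or not study drug was stopped (section 12.1.1).

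The size per affected patient is up to three antiplatelet drugs, duplicated aspirin, or twice the ticagrelor study dose; the last rests on the assumed open-label dose. Bleeding harm is possible, not certain. The textual conflict depends on none of these assumptions.

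**What to change.** - **5.6.6:** delete PCI from the examples, or limit the section to procedures that create no need for dual antiplatelet therapy, with a cross-reference giving 5.6.1 precedence for PCI or ACS that needs dual therapy.
- **5.6.1:** state that study drug is not restarted while dual therapy continues.
- **5.8.1 and 5.8.2:** carry the same exception in the bullet that points to 5.6.6, and add the dual-therapy stop to the list that matches its intended duration.
- **Sites:** send a letter stating the rule.

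The cost is wording in four sections and one site communication. Data collection and analysis do not change.
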